#### SECTION A. Monitoring Entity.

Considering the study rationale, population, procedures, and the risk: benefit profile as outlined, the overall risk level for participation in this study is classified as: **Minimum Risk.**

#### 2) Individual Roles and Responsibilities

*Principal Investigator, (PI).* As PI, **[name]** will overall be responsible for the immediate protection of all human participant study participants.

*Primary Mentor.* **[name]**, as [name] primary mentor on this K23 application, will serve as the senior individual responsible for providing oversight and guidance on [name] function as PI. Drs. [name] and [name] will discuss human subjects' participation and protections during mentoring meetings and as needed. [name] will provide guidance to [name] trial oversight and reviewing AE, as well as providing guidance on organizing SMC meetings and reports.

**[name]** is an independent investigator and an is Associate Professor at Medical University of South Carolina. She has a PhD and a background as a clinical psychologist with expertise in adolescent behavioral research. [name] has no real or apparent conflict of interest that would affect her performance in this role on the study. [name] will correspond semi-annually as part of the SMC to review de-identified cumulative AE study data to assess any impact on the safety of participants or on the ethics of the study. She will be responsible for reviewing all cumulative reported SAE related to study treatment. She will also review data safety monitoring reports generated by the biostatistician (BS) to provide study recommendations to the PI, MUSC's IRB and NINR. [name] will be notified within 24 hours of the occurrence of any SAE by the PI or project coordinator and will be provided with the necessary study information to provide an informed recommendation in real-time regarding the protocol and human participant safety.

**[name]** will be responsible for the classification of all reported adverse events (AE) and ensuring that all serious adverse events (SAE) are forwarded to the PI, her mentor, and the other members of the SMC within 24 hours and in compliance with MUSC IRB and NINR's reporting requirements. In addition, and in conjunction with the PI, the PC will be responsible for amending the protocol in accordance with SMC recommendations, submitting reportable SAEs to the IRB; and, submitting annual Progress Reports to the NIH/NINR through MUSC's OSRP. The PC will also be responsible for ensuring data management validation and verification of the electronic study research database, and the accurate reporting and timely notification of all AEs to the PI, and the other members of the SMC. As part of the SMC, the PC will be responsible for: conducting monthly internal quality control audits on all participant records and notifying the PI of any deficiencies; participating in data safety monitoring study management meetings; assisting in the generation of ad hoc participant data safety reports as requested; and, the forwarding of reportable SAEs to the NIH/NINR Program Official through MUSC's Office of Research and Special Programs (OSRP) within 72hrs of IRB review and acknowledgement.

**[name]** is the Director of Research at College of Nursing and a member of MUSC Institute of Human Values with Fellowship certification in Research Ethics. [name] has served and is currently serving as a member of numerous NIH/NINR RO1/R21/P20 DSM Boards and Committees, and FDA Industry Sponsored Clinical Trials. Additionally, he also has over 6 years of experience working on HRSA and PCORI funded demonstration programs and studies among patients with Sickle Cell Disease. With no study involvement, [name] has no apparent conflict of interest to serve in this capacity. [name] will be responsible for conducting semi-annual interim analyses, generating semi-annual AE safety reports from the electronic study research database and disseminating de-identified information to the other members of the SMC. The interim data analyses will only include safety related results; analyses in regard to study outcome will not be performed. The interim AE reports will provide typology, frequency data and outcomes of all reported and documented AE in the electronic study database. As part of the SMC, [name] will also participate in safety monitoring study management meetings.

## **SECTION B. Procedures for Safety, Risk and Confidentiality**

### **1) Monitoring Study Safety**

From the initial screening of the participant by inclusion and exclusion criteria to the informed consent process to the provision of participant study instruction to staff training in Good Clinical Practices (GCP) and regulations pertaining to the Conduct of Human Participant Research to weekly contact with participants to internal monthly quality control audits and protocol fidelity monitoring to the real-time review of AE by the SMC to the oversight of MUSC's IRB, procedures for monitoring study safety are consistently carried out throughout the study. Specific procedures include:

- Participants will be screened for inclusion and exclusion per the protocol; the PI or PC shall verify 100% of participants' eligibility prior to study enrollment through review of inclusion and exclusion criteria with potential participants.
- Participants will be fully informed as to all known risks and the possibility of risk from study participation in the informed consent process. These risks are minimal.
- Participants will be instructed to notify the researchers of any/all suspected or experienced adverse events whether they believe them to be related or not to the intervention.
- The PI or PC will track all reported participant AEs through to resolution. Please see Section C. 1 – 4.
- All investigators and research staff will maintain active CITI training.
- The PI or PC will maintain weekly contact with all participants to elicit information about AEs and to monitor participant study progress, compliance and safety.
- The PI or PC will review participants study logs for fidelity compliance with the intervention.

- The PI or PC will conduct a monthly internal quality control audit of all participant records to ensure compliance with MUSC IRB regulations; the PI and PC will work together to correct any errors.
- The PI and/or designee will observe and evaluate ten (10%) percent of eligibility screening visits, informed consents and study instructions performed by IRB approved study personnel and provide feedback and/or retraining of study personnel if fidelity to both applicable federal regulations and the protocol is not observed.
- The BS shall generate semi-annual AE reports for the PI, mentor, and the SMC to review.
- The SMC will have access to data on SAE within 24 hours and will be able to provide immediate recommendations to the PI, her mentor, and the PC.
- Investigator performance and compliance will be provided for through adherence to the MUSC IRB and Office of Research Integrity (ORI) Statement of Assurance and Policy 5.3: Education and Training Requirements for Individuals Involved in Human Research (<https://research.musc.edu/resources/ori/irb/policies>)

## **2) Minimizing Research-Associated Risk**

Diligent study data and safety monitoring will be conducted by the PI, mentor, PC, and the study's SMC throughout the conduct of this study in compliance with the following required elements of MUSC IRB's continuing review process:

1. Tracking and follow-up of participant accrual (including withdrawn consents) will minimize risk by identifying, disclosing, and mitigating any potentially unknown risk(s) of harm to study participants. These risks are minimal.
2. Timely and appropriate reporting of informed consent process deficiencies, protocol deviations, privacy breaches, conflicts of interest, and/or changes in personnel.
3. Ongoing soliciting, monitoring and appropriate reporting of adverse event activities.
4. Timely and appropriate IRB submission of safety-related documents such as audit reports, sponsor progress reports, SMC reports, and other materials or communications that might impact the safe conduct of this study.
5. Active cooperation with the IRB, sponsor, and other applicable entities in the event of a random or for-cause internal or external audit.

## **Institution-Wide Assurances**

This protocol will be conducted fully in keeping with the signed MUSC IRB Principal Investigator Statement of Assurance and Department Chair's Statement of Assurance, when submitted to the IRB as a required component of the MUSC IRB Human Research Review Application. Assurances include the following safety-related considerations:

## **3) Protecting Confidentiality of Participant data**

**Participant Screening and Enrollment.** All data from participants screened for the study will be entered into an electronic study database. Designated research staff will collect, gather, and enter required data (written informed consent, HIPAA Authorization, and demographics) onto study data forms. Screened patients who do not meet study eligibility will have specific screening data entered into the study database. The collected data will be helpful in examining the patient population and feasibility of enrollment criteria and will include reason for exclusion. All dates will be shifted and other Personal Health Information (PHI) will be removed from the study database upon study completion. All data obtained from this study will be used for research purposes only and will comply with Federal HIPAA regulations. Master Screening and Enrollment Logs will be maintained by the PI or PC and will be used by the PI or PC to prepare reports on accrual and attrition for the SMC.

**Case Report Forms.** All proposed study specific case report forms (source documents) for data collection will be designed by the PI or PC and, when possible, transferred by the PI or PC into electronic Case Report Forms (eCRFs) for use in the study's REDCap database. These study specific eCRFs source documents (study logs for correspondence, compensation and other forms such as pre-eligibility screens) will be coded by the participant's unique study ID# for all data collected including study instruments and will be maintained in the participant research record. Completed instruments that require signature on a paper CRF will be scanned and uploaded into the study database for remote electronic safety monitoring as well as maintained on file in accordance with MUSC policies and applicable Federal Regulations for the Conduct of Human Participant Research.

**Binders.** The PI or PC will prepare and maintain a participant-specific binder for each participant containing all non-eCRFs records. A regulatory file will also be maintained to include the IRB-approved Protocol, original Informed Consent documents, HIPAA forms and other study-related regulatory documents. All paper research records and CRFs will be maintained in a locked file cabinet, stored in a room for research files that is accessible only via a password protected entry system that features security cameras, within the MUSC College of Nursing. Access to the research records, study database and PHI will be restricted to study personnel as approved by the PI and MUSC IRB. As with all studies conducted at MUSC, this study is also eligible for a random audit by MUSC Office of Compliance.

**Data Processing.** This study will use Research Electronic Data Capture (REDCap) for data capture and management. REDCap is a software toolset and workflow methodology for the electronic collection and management of research and clinical trials data. REDCap provides secure, web-based, flexible applications, including real-time validation rules with automated data type and range checks at the time of data entry. Exports are made available for several statistical packages including SPSS, SAS, SATA, R and Microsoft Excel. The study-specific REDCap electronic database will be designed and developed by the PI or PC in concert with the BS. The provision of REDCap is made available through the South Carolina Clinical & Translational Research (SCTR) Institute at MUSC with NIH Grant awards UL1RR029882 and UL1TR000062.

**Data Security.** Ensuring data security, compliance with 45 CFR 46 and maintaining the integrity of PHI is a top priority. MUSC has Standard Operating Procedures (SOP) to ensure a high level of data security while coordinating electronic and paper data management activities for clinical research trials. The REDCap study database will be hosted in the Biomedical Informatics secure data center at MUSC, a secure environment for data systems and servers on campus, and includes firewall, redundancy, failover capability, backups and extensive security checks. The secure data center has strict access control; only authorized core personnel may access the facility un-escorted. Only authorized users are allowed to connect to the network, and the security of the network is actively monitored. Power and environmental controls have several layers of backups, from interruptible power supplies to alternate and redundant feeds to the local utility company. The REDCap system administrator contributes to the maintenance of institutional disaster recovery and business continuity plans. Load balancers and a highly fault tolerant SAN infrastructure contribute to high availability.

The REDCap system itself has several additional layers of protection including password protection. Access to the data and its security is managed institutionally by sponsored login IDs through a Shibboleth login with an MUSC issued NetID and features a user account management filter that controls who can access the data and to what degree. All personnel must pass an employment background check before being issued an ID. Password complexity, history and expiration standards are implemented at the institutional level. Access to individual REDCap projects and their data is managed by the owner of the project. All transactions are securely delivered to the application using Secure Sockets Layer (SSL – SHA-1 with RSA Encryption; 2048-bits). It is then transmitted internally (behind the firewall) to the database server. All transactions are logged at the server layer (httpd logging), application layers (REDCap logs activity to a database table), and the database layer, using both query

and binary logging. This feature provides audit trails for all changes, queries, data exports and reports. MUSC Information security policies are available at: <https://mainweb-v.musc.edu/security/policy/>

**Data Entry.** Only MUSC IRB approved study personnel that are authorized to have access to the REDCap study database will be granted password access. Study personnel using computers that are connected to the Internet will directly enter data into the remotely housed database. As such, no electronic study data will be stored on hard drives and/or any portable electronic devices. Additionally, all personnel with access to the database will have current University of Miami CITI training in the Conduct of Human Subject Protections, and HIPAA and Information Security trainings that are completed annually. Each participant will be assigned a unique study identifier, all PHI will be masked, and data exports will be limited to the PI, the mentor, the PC, or the BS for generating reports and the conduct of statistical data analysis.

**Data Monitoring.** Ongoing quality control procedures will be implemented for data collection, storage and processing. The PI or PC will conduct monthly monitoring of the study database and generate a report for review at team meetings. Standing agenda items for these meetings will include participant recruitment and retention, AE's, protocol deviations, data integrity and overall study conduct. The PI, mentor, and PC will work to resolve and validate discrepant data. Discrepancies that warrant clarification will be sent to appropriate parties for review and resolution. All data entry and changes made in the study database by authorized study personnel will be automatically logged by REDCap, and provide a transparent visible audit trail for reviewers.

### **SECTION C. Procedures for Identifying, Reviewing and Reporting Adverse Events**

**1) Identifying.** Potential minimum risks identified for participants are outlined in the Protection of Human Subjects section of the K23 grant application and are also outlined in the IRB-approved protocol and informed consent document. Additional unknown risks may occur and, if so, will be identified through diligent monitoring by the PI, mentor, or PC throughout the conduct of this study. During the informed consent process, participants will be advised of the potential risks of participation as identified in the IRB-approved informed consent document and reminded throughout the study that the researchers should be promptly informed about any concerns regarding potential side effects, adverse events, or clinical deterioration. Participants will also be instructed to notify the PI, PC, and/or designee of any suspected adverse events immediately if possible. All participants will be recruited via the MUSC Pediatric Sickle Cell clinic and will be current patients of the clinic. Therefore, if a participant notifies the PI or PC of an acute medical event, the participant will be advised to follow the usual processes of care as directed by his/her regular provider at the Pediatric Sickle Cell clinic. This may include calling the Pediatric Sickle Cell clinic during regular hours, calling the on-call provider after hours, or going to the emergency department if recommended by the regular provider. Throughout the course of study enrollment, the researchers will maintain weekly telephone and/or face-to-face contact with the all study participants to elicit information about experienced AE and to monitor participant progress. The PI or PC will maintain an electronic record of all reported adverse events and notify the SMC of all reportable events as they occur. The SMC will have real-time access to the study database to review and monitor all reported SAE that were reported as related to the intervention. The PI (with the mentor) or PC will generate and provide de-identified monthly administrative human subject safety reports for the SMC to review participant progress, accrual and attrition rates, and monitor the frequency of all reported side effects and AE. Additionally, the BS will generate and provide de-identified cumulative administrative human participant semi-annual safety reports for the SMC to review.

**2) Reviewing.** Adverse events will be assessed and graded by the members of the SMC according to the MUSC IRB Unanticipated Problems and Adverse Events Policies and Procedures, located at section 4.7 on the following webpage: <https://research.musc.edu/resources/ori/irb/policies>, and described below.

- **Expected/Anticipated**—Identified in nature, severity, or frequency in the current protocol, informed consent, investigator brochure, or with other current risk information.
- **Unexpected/Unanticipated**—Not identified in nature, severity, or frequency in the current protocol, informed consent, investigator brochure, or with other current risk information.
- **More Prevalent**—Occurs more frequently than anticipated or at a higher prevalence than expected.
- **Serious**—Results in death, is life threatening, requires inpatient hospitalization or prolongs existing hospitalization, results in persistent or significant disability/incapacity, cancer, overdose, or causes a congenital anomaly/birth defect.

The relationship of adverse events to study participation will be determined by the SMC according to the MUSC IRB Adverse Event Reporting Policy:

- **Unrelated**—There is not a reasonable possibility that the adverse event may have been caused by the drug, device or intervention.
- **Possibly Related**—The adverse event may have been caused by the drug, device, or intervention, however there is insufficient information to determine the likelihood of this possibility.
- **Related**—There is a reasonable possibility that the adverse event may have been caused by the drug, device or intervention.

**3) Reporting.** All reportable AE, SAE and unanticipated problems experienced by participants will be reported to the NIH/NINR and MUSC IRB in compliance with their Adverse Event Reporting Policy requirements, using the IRB's password protected on-line secure server adverse event reporting system. Within 24 hours after a reportable AE, SAE or unanticipated problem has been reported by the participant, it will be graded by the PI, her mentor, or PC, forwarded to the study's SMC for review, and then will be submitted by the PI to MUSC IRB. The Institutional Official(s) will review the event and discuss the report with the IRB Chair and the Director of the Office of Research Integrity. After IRB review and acknowledgement, the PI will further review, and the PI, her mentor, or PC will forward a copy of the reportable AE, SAE or unanticipated problem and IRB acknowledgement letter to the NIH/NINR Program Officer through MUSC's OSRP. The activities will be reported to the NIH/NINR within 72 hrs. In addition, all cumulative reportable AE, SAE and unanticipated problems included in the SMC reports will be submitted to the NIH/NINR in the PI's Annual Progress Reports.

**4) Examples of Potential Reportable Adverse Events.** In accordance with MUSC IRB Adverse Event Reporting Policy, an AE is reportable if it meets all of the following criteria: 1) is unexpected 2) is related and/or possibly related, and 3) is serious and/or suggests that the research places subjects or others at a greater risk of physical or psychological harm than was previously known or recognized. Additionally, per MUSC's policy all participant deaths, protocol deviations, complaints about the research, and breaches of confidentiality are reportable events. An example of an AE would be new onset of chest tightness and discomfort (symptom) that could potentially be associated with an acute exacerbation of the child's comorbid asthma. The participant's parent reported he/she recently ran out of his/her medication. The steps to be taken include withdrawing the subject from the study and inviting him or her to restart the study after symptoms subside. An example of an SAE would be the death of a participant from acute chest syndrome or stroke, which although would be viewed as unexpected and unrelated to the intervention is nonetheless a reportable serious event. No further steps would be taken except to review, grade and report the event. An example of an unanticipated problem would be the participant trips and falls while retrieving his/her phone to read a message from the provider. The steps in this case would be to report the event as per the IRB and NINR policy, and to discuss appropriate actions regarding whether the participant should remain in the study with the SMC. These events and problems will be reported in accordance with the IRB and NIH/NINR policy as noted in Section C.3.

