## 11.0 Data Management

**Sex as a biological variable.** We recruit equal numbers of male and female adolescents and preliminarily explore for differences by sex in outcomes, such as acceptability, satisfaction, communication content, symptoms, quality of life, transition readiness, and utilization by conducting preliminary subgroup analyses in preparation for the subsequent larger trial.

**Feasibility processes.** Variables will include those pertaining to study procedures as well as participant variables. Specifically, 95% confidence intervals for proportions will be used to estimate dichotomous outcomes including the proportion of YA, A/CG who agree to participate out of the number approached, the proportion adherent to the intervention protocol, i.e., providing daily symptom monitoring/tracking, using the education component, responding to messaging, lost to follow up, etc. For the continuous feasibility measures (length of time spent in app components), frequency distributions and the median and mean responses with 95% confidence intervals will be obtained. Benchmarks for feasibility success are recruitment rate of at least 2 YA or A/CG per week, retention rates of 70%, use of at least one component of the app  $\geq 2$  days per week (adherence), and expressed satisfaction in key informant interviews (37).

**Outcome measures and estimates of variability.** Secondary aim outcomes variables will include measures of symptoms (pain, fatigue, depression, anxiety, sleep interference), quality of life, transition readiness, and utilization (number of appointments kept, number of ED visits). Demographic and clinical variables obtained at baseline will be described via measures of central tendency (mean, median), variability and frequency distributions as appropriate. Additionally, demographic and clinical characteristics for those who adhered to the study protocol versus those who did not adhere (non-adherers and drop outs) will be compared to better describe the study population. For continuous quality of life measures, the difference between pre-and post-intervention measurements will be estimated via 95% confidence intervals. To assess preliminary intervention effects, we will conduct repeated measures ANCOVA with variables in individual models adjusting for “dose” defined as number of times each portion of the app was accessed, total time spent in each portion of the app, number of days symptoms were recorded, and number of A/CG-provider messages.

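### One adverse-event example withdraws a symptomatic participant from the study and restarts them later, where a pause in app use with continued calls and surveys would serve better (minor)

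*Combined protocol and SAP*

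**What the plan says.** Section C, item 4 (Examples of Potential Reportable Adverse Events) first sets the test for a reportable event: unexpected, at least possibly related, and one that "is serious and/or suggests that the research places subjects or others at a greater risk of physical or psychological harm" than was known before. It then describes a child with new chest tightness, possible exacerbation of asthma, and medication that had run out. For that case: "The steps to be taken include withdrawing the subject from the study and inviting him or her to restart the study after symptoms subside".

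Other parts of the protocol bear on this step:

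- Section C, item 1 (Identifying) already has a route for acute medical events: "the participant will be advised to follow the usual processes of care as directed by his/her regular provider at the Pediatric Sickle Cell clinic". Withdrawal is not mentioned there.
- The same item ties regular contact to being enrolled: "Throughout the course of study enrollment, the researchers will maintain weekly telephone and/or face-to-face contact".
- Section B, item 1 (Monitoring Study Safety) has adverse events tracked to resolution and refers staff to Section C, items 1 to 4.
- Section 13.0 (Withdrawal of Subjects) lists reasons for withdrawal. It does not separate stopping the app from leaving the study and describes no data collection afterwards.
- Section 10.0 obtains ED visits and clinic attendance in weekly phone checks. It sets surveys at baseline, 6 weeks, 12 weeks and 3 months after the intervention.
- Section 11.0 names symptoms, quality of life, transition readiness and "utilization (number of appointments kept, number of ED visits") as secondary-aim outcomes.

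**The concern.** The step ends participation in the study, not just use of the app, and what triggers it is a symptom. If calls and surveys stop with enrollment, later observations are missing for a reason tied to the outcomes being measured. The secondary aim is to estimate variability in symptoms, utilization and quality of life, so dropping unwell periods works against it.

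The restart raises a second issue. It is offered only once symptoms have subsided, and no baseline or calendar is given for it. A new baseline taken then would sit in a better health state and, for someone who had already used the app, would no longer be pre-intervention. Section 11.0 estimates pre-to-post differences in quality of life, so the choice of baseline matters.

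Against this, no benefit from ending phone calls and questionnaires is apparent. Section A says "the overall risk level for participation in this study is classified as" minimum risk, and the cause described in the example is a lapsed medication supply.

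**Working it through.** The plan gives no figure for this step, so there is nothing to reproduce. What can be sized is the loss for one participant under each reading of withdrawal and restart.

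**Inputs from section 10.0**

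- Enrollment of 6 months: a 12-week intervention plus 3 months of follow-up
- Three post-baseline surveys (6 weeks, 12 weeks, 3 months after the intervention)
- Weekly phone checks

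**Assumptions, not in the documents**

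- Three months is taken as 13 weeks.
- Weekly checks run either through all of enrollment or only through the intervention; both are shown.
- The event falls just after the week-6 survey.
- A temporary absence lasts 2 to 4 weeks.

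**Planned checks**

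- Through enrollment: 12 + 13 = 25
- Intervention only: 12

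**Reading 1: returns on the original calendar**

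- Checks missed: 2/25 = 8% to 4/25 = 16%. If calls last 12 weeks only, 2/12 = 17% to 4/12 = 33%.
- Return falls at week 6 + 2 = 8 to week 6 + 4 = 10, before the week-12 survey, so no survey is missed. An absence spanning a survey date would put that one survey at risk.

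**Reading 2: restarts the whole schedule**

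- All planned checks and surveys can still be collected, so no data need be lost.
- The new baseline would fall 8 to 10 weeks after the first, following 6 weeks of access to the app and recovery from the event. The schedule would end 8 + 25 = 33 to 10 + 25 = 35 weeks after first enrollment instead of 25. The protocol does not say which baseline is analyzed.

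**Reading 3: never returns (worst case)**

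- Checks lost: 25 − 6 = 19, and 19/25 = 76%. If calls last 12 weeks only, 12 − 6 = 6, and 6/12 = 50%.
- Surveys lost: 2 of the 3 post-baseline surveys.

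**Number of participants affected.** The documents give no rate for events of this kind, so neither the number withdrawn nor any bias can be calculated. The narrow reportability test and the minimum-risk rating suggest few.

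**Retention, for scale only.** Section 11.0 states: "Benchmarks for feasibility success are recruitment rate of at least 2 YA or A/CG per week, retention rates of 70" percent. If retention is counted per dyad or young adult and such a withdrawal counts as lost (both assumptions):

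- Dyads: 0.70 × 30 = 21 needed, so one withdrawal uses 1 of 9 allowed losses.
- Young adults: 0.70 × 15 = 10.5, so 11 needed; 1 of 4.
- Combined: 0.70 × 45 = 31.5, so 32 needed; 1 of 13.

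**The case against.** The strongest defense is that this is a single hypothetical. It follows a demanding test, while the general rules are usual care for acute events and the investigator's judgment of best interest. Neither requires withdrawal for illness. A reader might infer that becoming ill leads to withdrawal in this study; the documents do not support that, and the point is confined to the example.

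The loss of calls and surveys is also an inference. It rests on contact being tied to enrollment and on section 13.0 being silent, and silence does not prohibit follow-up. The invitation to restart implies some later contact, and the list of steps is not presented as complete. The consent pages are not in the public text and might say more. Tracking to resolution would probably capture the event itself, so it cannot be said that safety follow-up of that event is abandoned.

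Three further readings are tempting and should be resisted:

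- The 76% figure is not an expected loss. It combines no return, calls lasting 25 weeks and an event just after week 6.
- The example does not show that the retention benchmark is in danger. Section 11.0 does not define who counts as retained, nor whether a restarted participant belongs among "those who adhered to the study protocol versus those who did not adhere (non-adherers and drop outs"). Counting them as lost is an assumption, and the missing definition is a general gap not created by this example.
- The fall in the same item, where staying in the study is discussed with the safety committee, is labeled an unanticipated problem. Its different handling is not a contradiction.

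Finally, relieving a symptomatic child of study demands is a defensible caution, and this is a single-group feasibility study whose effect analyses are labeled preliminary. These arguments lower the weight of the point. They do not remove it: the example names withdrawal as a step, staff are referred to it, and no available text keeps planned follow-up going.

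**Conclusion.** The point holds as a minor one. Followed literally, the example makes either missing data or a second baseline depend on symptoms, in a study that measures symptoms and utilization, without an evident safety gain. The likely effect is small. With an absence of 2 to 4 weeks after the week-6 survey and return on the original calendar, 2 to 4 weekly checks and no survey are lost. With a full restart, the problem is an undefined baseline and calendar. Only permanent departure costs most of the remaining data. These sizes rest on the assumed timing, length of absence and duration of calls, and on the inference that planned follow-up stops at withdrawal. It is worth changing because the change is cheap, not because a conclusion of the study is at risk.

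**What to change.** In Section C, item 4, replace the step with: *advise usual care, pause app use if needed, and keep the participant (and caregiver) enrolled, discussing continued participation with the SMC if there is a safety concern.*

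In section 13.0, add: *A pause in app use for an adverse event is not study withdrawal. Unless the participant declines, calls and surveys continue on the original calendar with the original baseline.*

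The other withdrawal reasons in section 13.0, and the investigator's discretion, stay as they are. A sentence in section 11.0 saying that a paused participant who completes the remaining surveys counts as retained would be a useful but optional clarification.

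The cost is one replaced step and two added sentences. No new contact is needed, since the calls and surveys are already planned and surveys can be done by phone or online. The drawback is that some surveys of about 45 minutes would be completed while the participant is unwell, which the right to decline eases.
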